7.2.2 Visit 2 (week 2)

Provide a description of what procedures will be performed on visit 2 or day 2 or post-test in order of how these will be done. If your study involves more than two sessions or visits replicate this section for each additional session or visit (e.g., 7.2.3, 7.2.4, etc.).

This will occur during week 2 after surgery (with a window of 3 working days before or after depending on the patient schedule). Research team will evaluate healing progress of the participant and will report any AE. Research team will collect the diary and pedometer data. Research team will explain and demonstrate the new pad placement for the electrodes and the new settings of the electrical stimulation device (intervention group only). This should take about 10 minutes. This visit can be done via video call.

7.2.3 Visit 3 (week 4)

Provide a description of what procedures will be performed on visit 2 or day 2 or post-test in order of how these will be done. If your study involves more than two sessions or visits replicate this section for each additional session or visit (e.g., 7.2.3, 7.2.4, etc.).

This will occur week 4 after surgery (with a window of 3 working days before or after depending on the patient schedule). Research team will evaluate healing progress of the participant and will report any AE. Research team will collect the diary and pedometer data. Research team will explain and demonstrate the new pad placement for the electrodes and the new settings of the electrical stimulation device (treatment group only). This should take about 10 minutes. The Pedometer and the NMES device (if applicable) of the participant will receive and changes to the new device. This procedure will be done to check the memory of the devices with the values entered in the REDCap.)

7.2.4 Visit 4 (week 6)

Provide a description of what procedures will be performed on visit 2 or day 2 or post-test in order of how these will be done. If your study involves more than two sessions or visits replicate this section for each additional session or visit (e.g., 7.2.3, 7.2.4, etc.).

This will occur at week 6 after surgery (with a window of 7 working days after surgery depending on the patient schedule). Research team will evaluate healing progress of the participant and will report any AE. Research team will collect the diary and pedometer data. Participants will be instructed to discontinue the use of the NMES device. Subjects will fill out questionnaires and receive final an ultrasound imaging section. Participants must return both the NMES device and pedometer (activity monitor) at this visit. This should take about 1 hour.

7.2.5 Visit 5 (week 12)

Provide a description of what procedures will be performed on visit 2 or day 2 or post-test in order of how these will be done. If your study involves more than two sessions or visits replicate this section for each additional session or visit (e.g., 7.2.3, 7.2.4, etc.).

This will occur at a visit at week 12 after surgery (with a window of 3 working days before or after depending on the patient schedule). This is NOT part of the standard of care. Research team will evaluate healing progress of the participant and will report any AE. Research team will perform a heel-rise test. Subjects will fill out questionnaires and receive final an ultrasound imaging section. This should take about 1 hour.

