1.3 Secondary Study Endpoints

State the secondary endpoints to be measured in the study.

Muscle volume, Achilles tendon length and area, steps, and self-reported outcomes VAS (pain), ATRS, FAOS, PAS, adverse events, and compliance to the proposed treatment.

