Self-reported diary and outcomes: To evaluate frequency of loading, from the day after surgery, participants will complete a diary (paper or electronic survey via REDCAP) on estimated daily weightbearing load, number of steps/days with a pedometer placed at the hip, and pain on a visual analogue scale (VAS). Although standard of care prescribes no weight-bearing during the first two weeks after repair, patients are active during that period of time. The level of activity (steps), even though does not involve the use of the injured limb, can help explain potential differences in self-reported outcomes, especially kinesiophobia scores. These measurements are not part of the standard of care. Self-reported outcomes will be also collected at weeks 6 and 12: the Achilles tendon Total Rupture Score (ATRS) [56], the Physical Activity Scale (PAS) [57], the Foot and Ankle Outcome Score (FAOS) Quality of Life subscale [58], and the Tampa Scale of Kinesiophobia (TSK) [59], [60]. Patient reported outcomes (ATRS, PAS and FAOS) are part of the standard of care for Achilles tendon rupture.

Single heel-rise tests: The ability of performing a single heel-rise will be evaluated at week 12. The participants will stand on a flat box with the ankle in neutral position and will be asked to perform a single heel-rise. The participants will be classified as being able to perform a one-legged heel-rise if they were able to lift the heel at least 2 cm once while keeping the knee straight [60]. MuscleLab® (Ergotest Technology, Oslo, Norway) measurement system will be used for the evaluations as previously described in our previous study [29]. This will be performed in the physical therapy clinic at [name]. This test is not part of the standard of care for Achilles tendon rupture.

Table 3. Study Procedures for Stimulation and control groups

Week	Procedure
1	Consenting, Randomization, Distribution of diary and activity monitor, Demonstration of NMES (stimulation group only), (in-person visit)
2, 4	Adjustment of NMES (stimulation group only), collection of steps, and diary data. (Visit 2 can be done virtually with a video call, visit four should be done in person.)
6	Ultrasound Imaging, Questionnaires (ATRS, PAS, FAOS, TSK), collection of steps and diary data, Discontinue use of NMES (stimulation group only). (In-person visit)
12	Ultrasound Imaging, Heel-rise test, Questionnaires (ATRS, PAS, FAOS, TSK) (In person visit)

7.2.1 Visit 1 (Week 1).

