9.4 Frequency of data collection

Describe the frequency of data collection, including when safety data collection starts.

Data about tendon healing will be collected at 6, and 12 weeks. Pain, weight bearing, and step count will be recorded daily for the first 6 weeks. Heel-rise evaluation will be performed at week 12.

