10.0 Risks

List the reasonably foreseeable risks, discomforts, hazards, or inconveniences to the subjects related to the subjects' participation in the research. Include as may be useful for the IRB's consideration, a description of the probability, magnitude, duration and reversibility of the risks. Consider all types of risk including physical, psychological, social, legal, and economic risks. Note: Loss of confidentiality is a potential risk when conducting human subject research.

- If applicable, indicate which procedures may have risks to the subjects that are currently unforeseeable.
- If applicable, indicate which procedures may have risks to an embryo or fetus should the subject be or become pregnant.
- If applicable, describe risks to others who are not subjects.

Risk of Randomization: You will be assigned to a treatment program by chance. The treatment you receive may prove to be less effective or to have more side effects than the other research treatment(s) or other available treatments.

Heel-rise test: The heel-rise testing may cause local tendon pain. The subjects will be informed that if they have a pain level above a 5/10 they should inform the evaluator, stop the test, and avoid strong physical activity for 1 or 2 days.

NMES usage: The device used for this test is FDA approved. There is a minimal risk of infection. Discomfort during and muscle soreness after usage lasting a few days after the test may be experienced. Skin irritation caused by the adhesive pads may also occur. Excessive pain might occur during stimulation, even at the recommended settings. Subjects will be instructed to gradually increase the stimulation intensity up to the recommended level by PT. Subjects will be instructed to contact the research team if the excessive pain occurs at or below the recommended intensity.

Tendon healing: Re-injury of the tendon is also a potential risk. The rate of tendon re-rupture in standard therapy is estimated between 2% and 5% [64]. Gapping or non-healing of the tendon have also been observed in regular therapy. These adverse events may be observed in the participants participating in the study. Statistical analysis will be performed to determine if the risk of these adverse events is higher in the intervention group compared to standard therapy.

Additional Risks

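### The week-12 assessment order is not fixed: questionnaires are listed after the heel-rise test in both places, and the two listings disagree on when ultrasound is done

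*Combined protocol and SAP*

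**What the plan says.** **Week-12 visit text (section 7.2.5).** The form's prompt asks for procedures "in order of how these will be done". After the healing and adverse-event check, the answer reads "Research team will perform a heel-rise test. Subjects will fill out questionnaires and receive final an ultrasound imaging section". The visit is expected to take about an hour.

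**Table 3 (section 7.2).** The week-12 row reads "Ultrasound Imaging, Heel-rise test, Questionnaires (ATRS, PAS, FAOS, TSK) (In person visit". The table does not say whether a row is a sequence or just a list.

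**The test.** A participant passes if "able to lift the heel at least 2 cm once while keeping the knee straight" (section 7.2). Section 10.0 states: "The heel-rise testing may cause local tendon pain".

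**Secondary endpoints (section 1.3).** "Muscle volume, Achilles tendon length and area, steps, and self-reported outcomes VAS (pain), ATRS, FAOS, PAS, adverse events, and compliance to the proposed treatment". TSK and shear wave elastography are both collected under section 7.2, but neither is in this list.

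**Blinding.** Section 7.4.5 marks blinding as not applicable, and section 17.4 has participants told their allocation.

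No section fixes the week-12 order, sets a rest interval after the test, or asks for the order to be recorded.

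**The concern.** ATRS, FAOS and PAS are self-reported and come from participants who know their arm. If they are completed after the heel-rise test, the participant has just learned whether the heel could be lifted and may have some tendon pain from trying. Answers on function, quality of life or fear of movement could then partly reflect the test and not the preceding weeks of recovery.

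What is at stake is how independent these secondary outcomes are from the primary one. If answers respond to passing or failing, part of any arm difference in the scores repeats the primary result. This is hard to undo in the analysis. The test result is itself the primary outcome, so adjusting the scores for it would also remove real treatment effect, and the order is not recorded.

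For ultrasound the issue is consistency. The scan may come before the test for some participants and after it for others, depending on which listing staff follow.

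**Working it through.** **Step 1. The two week-12 listings side by side.**

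- Section 7.2.5: heel-rise test, questionnaires, ultrasound.
- Table 3: ultrasound, heel-rise test, questionnaires.

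Questionnaires come after the test in both. Ultrasound is after the test in the first and before it in the second.

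**Step 2. Is either listing a reliable sequence?**

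- Section 7.2.5 sits under a prompt that asks for order. However, its questionnaire and ultrasound sentence repeats the week-6 sentence in section 7.2.4, "Subjects will fill out questionnaires and receive final an ultrasound imaging section", so it may simply have been carried over.
- The week-6 row of Table 3 gives ultrasound, questionnaires, steps and diary, stop NMES. Section 7.2.4 gives diary and pedometer, stop NMES, questionnaires, ultrasound. That is nearly the reverse, so the table and the visit text cannot both be sequences.
- Section 7.2.1 has a similar prompt. It mentions the NMES demonstration before allocation is communicated, although Table 3 limits the demonstration to the stimulation group. That text is not strictly chronological either.

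The order is therefore unspecified. Whichever listing staff follow literally, the questionnaires come after the test.

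**Step 3. Which readouts can be exposed?**

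- Exposed if they follow the test: week-12 ATRS, FAOS, PAS and TSK, and the week-12 ultrasound.
- Not exposed: diary pain and steps (section 9.4: "Pain, weight bearing, and step count will be recorded daily for the first 6 weeks"), NMES compliance, and all week-6 questionnaires and scans. No heel-rise test takes place before week 12.
- Not exposed: the primary endpoint, which is the test itself.

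**Step 4. Size of a between-arm artefact in a questionnaire score.** The plan states no figure to reproduce. The inputs are the section 8.2 design rates of passing: 0.50 in control and 0.85 with NMES. Let c be a shift the test causes in everyone and d the extra shift in those who pass relative to those who fail. Both are assumptions, taken to be the same in each arm.

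- Mean shift in control = c + 0.50d
- Mean shift with NMES = c + 0.85d
- Artefactual arm difference = (0.85 − 0.50)d = 0.35d

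Results in units of the score:

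- c = 1, d = 0: shifts 1.00 and 1.00, difference 0.
- c = 0, d = 1: shifts 0.50 and 0.85, difference 0.35.
- c = 0.5, d = 0.5: shifts 0.75 and 0.925, difference 0.175.
- For scale only, d = 5 gives 0.35 × 5 = 1.75 and d = 10 gives 0.35 × 10 = 3.5.

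The common part c drops out. If the arms have equal pass rates, the difference is 0 × d = 0 for any d.

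**Step 5. Direction.** If failing makes people score themselves worse, the difference favours NMES. If a completed lift causes pain that worsens the score, more NMES participants are affected and the difference goes against NMES. The documents do not say which applies.

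**The case against.** The strongest reply is that the plan leaves the order open and does not prescribe questionnaires after the test. Step 2 supports this, and it stands. It does not remove the problem, because nothing in the plan puts the questionnaires first.

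A reader might go further and infer several things that the documents do not support:

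- **That the week-12 secondary data are contaminated.** No section says that one lift of at least 2 cm changes ATRS, FAOS, PAS, TSK, tendon length or area, or elastography. Section 10.0 says only that pain is possible. Carry-over is a possibility, not a finding.
- **That any bias favours NMES.** Two opposite mechanisms are plausible (step 5), and no shift is given. Participants may already know what they can do, in which case the shift could be zero.
- **That sites use different orders.** Section 17.3 says both locations follow the same protocol, and section 15.5 says ultrasound protocols will be agreed. Conflicting listings allow the order to vary; they do not show that it does.
- **That week-6 to week-12 comparisons are spoiled.** Section 8.3 plans no change analysis between those visits, and both arms take the same test.

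It is also fair to say that TSK and elastography, which might seem the most sensitive readouts, are not listed secondary endpoints. A further practical objection also stands: putting the primary test last in a one-hour visit makes it the item most at risk if time runs short.

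**Conclusion.** The point holds as a minor one. Sections 7.2 (Table 3) and 7.2.5 conflict on where ultrasound falls and must be reconciled. Both list the questionnaires after the heel-rise test, so carry-over to week-12 ATRS, FAOS, PAS and TSK is possible and uncontrolled.

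The between-arm effect is zero if the test affects everyone equally, and 0.35 times the shift if it depends on the test result. The 0.35 rests on the 50% and 85% design rates and on the shift being the same in both arms. The shift itself is unknown in size and sign and may be zero, so no numerical bias should be quoted as an estimate.

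The ultrasound part is weaker still, because the load is a single small lift and Table 3 already puts the scan first.

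**What to change.** State one week-12 order in both section 7.2.5 and Table 3, for all sites: questionnaires first, then ultrasound, then the heel-rise test. Say explicitly that it is a sequence. This is the questionnaire-then-ultrasound order already written for week 6 in section 7.2.4, with the test added at the end. Add a field to the case report form to record the order actually followed.

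The cost is wording in two places, one form field and a reminder to staff. It needs no extra visit, procedure or personnel.

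The one downside is that the primary test comes last. Section 7.2 places the test in a physical therapy clinic and the scan in a radiology suite or laboratory, so the visit must be scheduled to leave protected time for the test. This matters because section 8.2 needs 22 per group and 25 are planned, a margin of 25 − 22 = 3 per group.

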1.2 Primary Study Endpoints

State the primary endpoints to be measured in the study.

Clinical trials typically have a primary objective or endpoint. Additional objectives and endpoints are secondary. The endpoints (or outcomes), determined for each study subject, are the quantitative measurements required by the objectives. Measuring the selected endpoints is the goal of a trial (examples: response rate and survival).

The primary outcome of this study is to measure the ability of participants to perform a heel rise at week 12, which is a strong predictor of long-term outcomes.

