9.2 Data that are reviewed

Describe the data that are reviewed, including safety data, untoward events, and efficacy data.

Achilles tendon healing:

- re-rupture
- deep vein thrombosis
- deep and superficial infection

NMES:

- skin irritation
- excessive pain

Benefits/efficacy:

- self-reported outcomes (questionnaires)
- daily step count
- ability to perform a heel-rise

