17.4 Subject Enrollment

Describe the procedures for coordination of subject enrollment and randomization for the overall project.

Clinicians collaborating in the study will identify patients at the moment of diagnosis with a complete Achilles rupture and undergoing an Achilles repair surgery at the sports medicine clinic. Clinicians will hand out the study flier and briefly mention to the patient that they may be eligible for a research study. The flier will include a QR code that will direct patients to a YouTube video where more information about the study is provided. If the participant is interested, the PI and/or a member of the team will provide an electronic copy of the informed consent for the patient to read. At the post-surgery appointment, a member of the team will discuss any details of study with the participant and will answer any questions they may have. Then the screening questions will be asked, and participants will sign the informed consent if eligible to participate.

Participants will be randomly assigned to a NMES treatment or control group in a 1:1 ratio. The Statistician will be responsible for generating a master list for each site with patient codes will be prepopulated with randomly assigned treatments (NMES vs control). As recruitment is performed, patients will be assigned a code with the corresponding intervention. The randomization will be performed at a 1:1 ratio between control and stimulation group.

Method:

1. The Statistician will generate one mutual master list (for State College and for the University of Delaware).
2. The master list will be shared with the team members in charge of recruitment through REDCap.
3. Once a subject is recruited (screened and consented), the next available code from the list will be assigned.
4. The patient will be then notified of the type of treatment they will get.

The master list will be stored and available in REDCap.

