20.1 Data and/or specimens being stored

Identify what data and/or specimens will be stored and the data associated with each specimen.

Identifiable data include: Informed consent, master list with codes, contact information. De-identified data include: ultrasound images, questionnaires, pedometer data, heel-rise tests, and pain data. No specimens are collected in this study.

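### No masking of outcome assessment is specified in this open-label trial, and with about 22 per arm a single heel-rise classification can decide the primary result

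*Combined protocol and SAP*

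**What the plan says.** Section 1.2 makes the primary outcome to "measure the ability of participants to perform a heel rise at week 12". Section 7.2 defines a pass as being "able to lift the heel at least 2 cm once while keeping the knee straight", and says that the MuscleLab "measurement system will be used for the evaluations as previously described in our previous study". Section 7.2.5 assigns the test: "Research team will perform a heel-rise test".

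The same term, research team, is used for those who demonstrate NMES at week 1 (7.2.1) and re-instruct on pads and settings at weeks 2 and 4 (7.2.2, 7.2.3). It is also the only staff named at the week-6 visit, where the device is returned and the first ultrasound is done (7.2.4). Controls receive standard rehabilitation without NMES (7.1).

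Section 7.4.5, on blinding of the test article, is answered as not applicable, as is 18.7 on unblinding. Neither addresses outcome assessors, and no other section does.

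Section 17.4 shares the randomisation list with recruiting staff and adds: "The master list will be stored and available in REDCap". Outcome data also go through REDCap (15.5, 17.3). Section 7.2 gives the ultrasound sites and acquisition method but names neither operator nor reader. Section 20.1 lists what is kept: "De-identified data include: ultrasound images, questionnaires, pedometer data, heel-rise tests, and pain data".

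**The concern.** Participants in a no-sham stimulation trial cannot be blinded, so masking the assessor is the main protection left for a performance test. The plan does not say whether the person who decides pass or fail knows the arm, and its wording allows that person to have taught the participant NMES.

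The height threshold is fixed and measured. These matters are left to the tester on the day:

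- whether the knee stayed straight;
- how many attempts are offered;
- how much encouragement is given;
- whether an attempt counts, including a test stopped for pain, which section 10.0 allows without saying how it is scored.

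A tester who expects NMES to help could, without intent, treat borderline cases differently by arm. The primary analysis compares two proportions in a small sample, so a few such calls could create or remove the trial's positive finding. The ultrasound measures, which are secondary, have the same gap because no masked reading is stated.

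**Working it through.** **Inputs.** Section 8.2: 50% passing in control, 85% with NMES, 80% power, 5% level, 1:1 allocation, 22 per group, 10% attrition, 25 per group. Section 8.3: improvement is significant if the lower 95% confidence limit of the odds ratio exceeds 1. The plan does not name the interval method. I assume the usual Wald interval on the log odds ratio, adding 0.5 to each cell when one is zero.

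**1. The plan's own sample size.** With the pooled formula, n = [z(α)·√(2·p̄·q̄) + z(β)·√(p1q1 + p2q2)]² / d², where p̄ = 0.675, q̄ = 0.325 and d = 0.35.
- One-sided 5%: (1.645 × 0.6624 + 0.8416 × 0.6144)² / 0.1225 = 21.07, so 22. Then 22 / 0.9 = 24.4, so 25. This matches the plan.
- Two-sided 5%: (1.960 × 0.6624 + 0.8416 × 0.6144)² / 0.1225 = 26.90, so 27.

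The stated 22 therefore reproduces one-sided only. That is a separate matter and is not used here. Masked assessment changes no input to this calculation.

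**2. How many classifications separate success from failure?** Take 11/22 passing in control. The rule is ln(OR) − 1.96·SE > 0, with SE = √(1/a + 1/b + 1/c + 1/d).
- NMES 17/22: OR = (17 × 11)/(5 × 11) = 3.4. SE = √(1/17 + 1/5 + 1/11 + 1/11) = 0.664. Lower limit = exp(1.224 − 1.301) = 0.93. Rule not met.
- NMES 18/22: OR = (18 × 11)/(4 × 11) = 4.5. SE = √(1/18 + 1/4 + 1/11 + 1/11) = 0.698. Lower limit = exp(1.504 − 1.368) = 1.15. Rule met.

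One participant changes the conclusion.

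**3. Illustration of differential scoring.** Suppose the true pass rate is 50% in both arms and a share m of truly unable NMES participants is recorded as able, so that the observed NMES rate is 0.5 + 0.5m. The documents give no value for m; every value below is an assumption. Of 22 participants, 11 are expected to be truly unable, so m = 10% is about one person. Summing the two binomial distributions exactly over all outcomes that meet the rule, with 22 per arm:

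| m | Observed NMES rate | P(false significant improvement) |
|---|---|---|
| 0 | 0.500 | 0.0244 (2.4%) |
| 5% | 0.525 | 0.0355 (0.03549, 3.5%) |
| 10% | 0.550 | 0.0503 (5.0%) |
| 20% | 0.600 | 0.0943 (9.4%) |

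With 25 per arm the figures are 2.2%, 3.4%, 5.0% and 10.0%. If able controls were also recorded as unable at the same rate, 22 per arm would give 5.1% at m = 5% and 9.5% at m = 10%.

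**The case against.** The strongest reply is that the protocol nowhere says the assessor is unmasked. Research team is a generic label in a study with more than one site. The heel-rise test takes place in a physical therapy clinic, and section 17.4 shares the list with recruiting staff rather than with everyone. The pass criterion is fixed and instrumented, which narrows the room for bias. The misrecording shares have no source. All of this stands, and it limits what can be claimed.

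A reader might infer four stronger things that the documents do not support:

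- **That the tester knows the allocation.** This is a reasonable inference from the shared label and open design, but no section identifies the individual tester. What is established is that masking is not specified.
- **That the NMES team reads the ultrasound, tracing by hand.** No operator or reader is named, and section 7.2 does not say how areas are measured on the image.
- **That masking would cost nothing.** No section gives staffing or cost. Separating the tester from the person who delivered NMES takes scheduling effort and may not be possible at each site.
- **That re-scoring stored records would cure the problem.** A height trace contains the part that is already objective. Knee position, encouragement and probe placement happen live, no video is planned, and section 20.1 does not say what a stored heel-rise test contains.

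Sections 9.2 and 9.6 also put "ability to perform a heel-rise" into a two-monthly cumulative review. Seeing earlier results does not reveal the arm of the next participant, so I place no weight on that.

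These limits leave the omission itself in place: the plan neither names a masked assessor nor standardises the live parts of the test.

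**Conclusion.** The concern holds as a gap in specification. It does not show that assessment is biased. The staff label that covers NMES delivery also covers the primary test, the list and the outcomes share a data system with no stated separation of access, and nothing in the plan provides masked scoring.

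The firm part of the size is fragility: under the plan's rule, one classification out of 22 can decide the result at a plausible control count. The false-positive figures show sensitivity only. They assume no true effect, 50% passing in both arms, errors favouring NMES only, a Wald interval and invented error shares. A 10% share roughly doubles the one-directional error rate. The documents cannot say whether the real share is larger, smaller or zero.

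The protocol should be changed on this point, because partial protection is available without altering the sample size, visits or procedures.

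**What to change.** Amend sections 7.2, 7.2.5 and 7.4.5 to state that participants and treating staff are unblinded, and how outcome assessment is protected:

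1. Use a written heel-rise script with fixed instructions and encouragement and a fixed number of attempts. Set in advance what makes an attempt valid, and how a test stopped early is scored.
2. Where staffing allows, have the week-12 test run by an existing team member who did not deliver NMES to that participant and whose REDCap rights exclude the allocation list. Record when this was not possible.
3. Keep the MuscleLab trace under the study code and derive the 2 cm classification from it, masked to arm. Measure ultrasound images from coded files, also masked to arm.

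The cost is protocol wording, a change to REDCap user rights, and some scheduling and file-handling effort. No new procedure is needed and the sample size stays the same. Masking will be partial: knee position and probe placement are still judged live, and unblinded participants may disclose their arm or differ in effort. The report should say so.
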